Primary hypotheses: Our primary measure of temporal window is delay discounting (DD). Our primary measure of alcohol consumption is self-reported drinks per day. Participants are asked to report how many standard drinks they had for the previous 24 hours on each day of the 7 day baseline and 28 day intervention period. Our secondary measure of alcohol consumption is breath alcohol samples from the remote breathalyzer. Participants will provide three breath samples daily for the 7 day baseline and 28 day intervention period. Our primary measures of demand are alpha and Q0. Alpha and Q0 are two derived outcomes from a hypothetical alcohol purchase task. Participants are asked to report the number of standard drinks they might hypothetically purchase at increasing price points. Q0 is a measure of how many drinks a participant might purchase when drinks are free (price = \$0). Alpha is a measure of the participants sensitivity to increasing prices (i.e., how quickly they decide to stop purchasing at higher prices). Our measure of craving is the Alcohol Urges Questionnaire (AUQ). Our measure of neural activity is BOLD response. We hypothesize that baseline BOLD response will be predictive of the efficacy of the intervention. We will model our primary outcome measures using a mixed-effects hierarchical model that includes day, time (pre/post intervention), and intervention group. A random effect will be included for each participant. We will include baseline BOLD response as a fixed-effect covariate in our analysis.

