14.0 Number of Subjects

14.1 Indicate the total number of subjects to be enrolled and how this number was determined (e.g., sample size calculation [show], number of available subjects in a finite pool, number of tests funding award would allow):

Although we have observed large effect sizes of EFT on DD in AUD participants in our preliminary studies (pre-post $d=1.6$; post-only $d = 0.68$), we used a more conservative medium effect size ($f= 0.25$) to inform sample sizes to increase power to detect effect on the broader range of measures proposed here (e.g., intensity of demand). Using the method proposed by Borm, Fransen, and Lemmens, and a pre- and post-measurement correlation of 0.70218, 76 total participants would be needed to complete this study (38 participants per group), assuming a type 1 error rate of 0.01 and 95% statistical power, based on an ANCOVA comparing the intervention while using the baseline measure as a fixed-effect covariate in the analysis.

We have been successfully recruiting individuals with AUD in our community for the past 8 years. Based on these 8 years of experience recruiting alcohol users into studies of comparable length and complexity, we anticipate that over 80% of consented participants will be eligible (i.e., randomized) and about 65% of those eligible individuals will complete this study. Thus, to achieve a final sample size of 76, we anticipate consenting 200 participants. We plan to enroll more than our average attrition rate because of the increased procedures and the time demands of the study.

14.2 If this is a multi-site study, indicate the number of subjects to be enrolled at this site and the total to be enrolled from all sites:

N/A

14.3 If applicable, indicate the number of potential subjects you expect to screen for enrollment, and the number of subjects you will need to complete the research procedures:

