Although we have observed large effect sizes of EFT on DD in AUD participants in prior pilot studies (pre-post $d=1.6$; post-only $d = 0.68$), we used a more conservative medium effect size ($f=0.25$) to inform sample sizes and increase our power to detect effect on the broader range of measures proposed here (e.g., intensity of demand). Using a repeated measure correlation of 0.5, 52 total participants would be needed to complete this study (26 participants per group), assuming a Type I error rate of 0.01 and 80% statistical power, based on repeated measures within- between interaction ANOVA with 2 groups and 2 measurements.

Data Measures

Demographics

Demographic measures collected include age, sex, gender, ethnicity, and race.

SES

Education level, income, occupation/working status, household members

Delay discounting

To measure DD, the hyperbolic discounting model³⁸ will be fit to participants' indifference points across delays: $V=A/(1+kD)$ in which V is the immediate subjective value of the delayed option, A is its objective amount, D is its delay, and k is the only free parameter, indexing rate of discounting (larger k implies greater delay discounting, and a shorter temporal window). The discounting rate k will be log transformed to approach normality and stabilize the variance. Analysis will proceed by fitting the above equation to individual

subject data, then comparing values of discount rate $\ln(k)$ between experimental groups, as described above. We will compare fit to the hyperbolic model in comparison to alternative models as part of our third Objective.

Demand measures

To obtain dependent measures of demand, participants' data from the alcohol purchase task will be fit to a modified³⁹ exponential equation of the demand function¹⁸ to quantify the relationship between the price of alcohol and consumption: $Q=Q_0 \times 10^{k(\exp(-\alpha Q_0 C)-1)}$ where Q is consumption of the commodity, C is the price, Q_0 is the derived initial consumption without cost constraints (demand intensity), k is the span of the function in logarithmic units, and α is the demand elasticity. Values of k are set to a constant determined empirically by the actual data, leaving Q_0 and α as free parameters to be fit. Note that although the delay discounting model and the demand equations use k , they refer to different variables. Dependent measures will be compared between experimental groups, as described above.

Resting state fMRI

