We will use a 3T Siemens MAGNETOM Prisma^{fit} scanner (Siemens, Erlangen, Germany) with a 20-channel head/neck coil. T1-weighted images will be acquired at $1 \times 1 \times 1 \text{ mm}^3$ resolution using 3D MPRAGE, FOV = $256 \times 256 \times 176 \text{ mm}^3$, TR/TE/TI = 1950/4.44/950 ms, FA = 12° , phase partial Fourier 7/8, slice partial Fourier 6/8, GRAPPA factor = 4 with 33 reference lines, and bandwidth = 140 Hz/pixel. Functional BOLD data will be acquired using EPI with thirty-three 4 mm interleaved slices with a 10% slice gap, TR/TE = 2000/30 ms, FA = 10° , in-plane resolution of $3.4 \times 3.4 \text{ mm}^2$, anterior-to-posterior phase encoding and a bandwidth = 2442 Hz/pixel. Participants will be instructed to keep their eyes open during the scan and direct their gaze on a white plus (+) sign centered on a black background.

Alcohol Consumption

Changes in drinks per day and the number of positive breath alcohol samples (BrAC) will be compared within subjects between pre-intervention and post-intervention. In

addition, differences in drinks per day and the number of positive BrAC samples will be compared between groups (EFT and CET). A Timeline Follow Back (TLFB⁴⁰) will be conducted during Session 2 (pre-intervention) and Session 6 (1-month follow-up) to assess the number of alcoholic drinks consumed daily for the past 30 days. During the intervention period (from Session 2 to Session 5), participants will report daily the number of alcoholic drinks consumed.

Alcohol Urges Questionnaire (AUQ)

The Alcohol Urges Questionnaire ⁴¹ will be used to assess craving for alcohol. This 8-question measure of drinking urges is scored by summing responses to a 7-point Likert scale. The dependent measure of the summed score will be compared within subjects between pre-intervention and post-intervention. In addition, differences in alcohol craving will be compared between groups (EFT and CET).

Alcohol Use Disorders Identification Test (AUDIT)

The Alcohol Use Disorders Identification Test (AUDIT⁴²) will be used to assess hazardous or harmful alcohol use. AUDIT is a 10-item screening tool that assesses alcohol consumption, drinking behaviors, and alcohol-related problems. Differences in alcohol AUDIT scores will be compared between groups (EFT and CET).

Alcohol Relative Reinforcement Schedule (ARRS)

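### The SAP names no model or tested term for ln(k), Q0, alpha and AUQ, and the documents offer three unreconciled forms of analysis

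*SAP*

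**What the plan says.** Protocol 5.2 names delay discounting as the primary measure of temporal window, alpha and Q0 as the primary measures of demand, and AUQ as the measure of craving. All four fall under SAP Objective 1. The documents say the following about how they will be analysed.

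- **SAP, Data Measures, Delay discounting:** the discounting equation is fitted to individual "subject data, then comparing values of discount rate $\ln(k)$ between experimental groups, as described above".
- **SAP, Data Measures, Demand measures:** "Dependent measures will be compared between experimental groups, as described above".
- **SAP, Data Measures, AUQ:** the summed score is compared pre to post within participants and, separately, between groups. No model is given and there is no cross-reference.
- **SAP, Statistical Analyses, Objective 1:** a generalized linear mixed model for daily drinks (Poisson, or another distribution if overdispersed) and a similar analysis of positive or negative breath results. Nothing is stated for ln(k), Q0, alpha or AUQ. Secondary outcomes are to follow the primary hypothesis by analogy.
- **SAP, Sample size:** 52 completers, "based on repeated measures within- between interaction ANOVA with 2 groups and 2 measurements".
- **Protocol 5.2:** the primary outcomes are modelled with a "mixed-effects hierarchical model that includes day, time (pre/post intervention), and intervention group", plus a participant random effect and baseline BOLD response.
- **Protocol 14.1:** 76 completers, "based on an ANCOVA comparing the intervention while using the baseline measure as a fixed-effect covariate in the analysis".

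**The concern.** The SAP's cross-reference for ln(k) and demand points upward, but Data Measures comes before Statistical Analyses, so no analysis section lies above it. The only test named there is the basis of the sample-size calculation. Reading downward does not help either: the Objective 1 models are for counts and binary results, whereas ln(k) is log-transformed precisely so that it can be treated as roughly normal.

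The protocol adds two further forms. Its mixed model names no group-by-time term and no baseline value of the outcome. Its sample-size section assumes ANCOVA on the outcome's baseline. A reader therefore cannot tell which coefficient decides whether EFT changed delay discounting relative to CET. The candidates differ in power, and one of them differs in what it estimates. While the choice stays open, it can be made after the results are seen.

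**Working it through.** **Inputs.** From SAP, Sample size: f = 0.25, correlation ρ = 0.5, alpha 0.01, target power 80%, n = 26 per group (N = 52). From SAP, Statistical Principles: analysis alpha 0.05. Assumptions: equal expected baselines (randomisation), equal pre and post variance (set to 1), complete data.

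**Reproducing the SAP's 52.** For the within-between interaction with m = 2 measurements, the noncentrality is λ = f²·N·m/(1 − ρ), with 1 and N − 2 degrees of freedom.

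- N = 50: λ = 0.0625 × 50 × 2 / 0.5 = 12.5; power 79.9%.
- N = 52: λ = 0.0625 × 52 × 2 / 0.5 = 13.0; power 81.8%.

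So 52 is the smallest even total that reaches 80%. Under this formula, f = 0.25 corresponds to a group difference in change of δ = 4f = 1.0 SD. As a check, δ²(n/2)/[2(1 − ρ)] = 1 × 13 / 1 = 13.0, the same λ.

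**The four candidate tests on those inputs.** In each case λ = (effect estimated)² × (n/2) / (variance per participant), with n/2 = 13.

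| Test | Effect estimated | Variance per participant | λ | Power, alpha 0.01 | Power, alpha 0.05 |
|---|---|---|---|---|---|
| ANCOVA on baseline | δ = 1.0 | 1 − ρ² = 0.75 | 17.3 | 92.6% | 98.3% |
| Group-by-time interaction | δ = 1.0 | 2(1 − ρ) = 1.0 | 13.0 | 81.8% | 94.2% |
| Post-only, unadjusted | δ = 1.0 | 1.0 | 13.0 | 81.8% | 94.2% |
| Group coefficient, time + group only | δ/2 = 0.5 | (1 + ρ)/2 = 0.75 | 4.3 | 28.7% | 53.3% |

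The last row arises because, with no product term, the group coefficient averages the pre-intervention difference (expected value 0) and the post-intervention difference (δ): (0 + δ)/2. That model would need about 144 completers for 80% power at alpha 0.01.

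**Simulation.** In 300 simulated trials (N = 52, ρ = 0.5, true difference 1.0 SD) fitted as random-intercept models, the additive group estimate averaged 0.50 SD in size, with 34% rejections at 0.01. The interaction estimate averaged 1.01 SD, with 86% rejections. The fits used large-sample p-values, so rejection rates run somewhat above the exact figures.

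**Sensitivity to the correlation.** Taking the protocol's value as about 0.70, with n = 26 and δ = 1.0:

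- ANCOVA: 13/0.51 = 25.5
- interaction: 13/0.60 = 21.7
- post-only: 13.0
- additive group coefficient: 0.25 × 13/0.85 = 3.8

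The ranking is unchanged, except that post-only now falls behind the interaction.

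**Sensitivity to sample size.** At the protocol's N = 76 with ρ = 0.5, δ = 1.0 and alpha 0.01, power is 99.0% for ANCOVA, 95.4% for the interaction and 45.4% for the additive coefficient.

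**The case against.** The best defence is that the intended contrast can be inferred. The SAP's sample-size paragraph, just above the cross-reference, names a 2 × 2 within-between interaction, which is a sound contrast. For ARRS, the Contemplation Ladder and PACS (another craving scale), the SAP says that change from before to after the intervention is compared between groups. The protocol says its model includes day, time and group. It does not say main effects only, does not exclude a product term, and does not name the group coefficient as the test. The same sentence also has to serve daily drinks, where day is a natural term.

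Most of this stands, and it limits the point. A reader might infer that the trial will test the wrong contrast. The documents do not support that: the additive reading is one possible reading of an incomplete list. A reader might also infer that any unadjusted comparison loses power against the SAP's plan. At ρ = 0.5 it does not, because the post-only score and the change score have the same variance.

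Nor should power figures near 6% be quoted as the cost of this gap. They come from taking the true difference as 0.5 SD, which at N = 52 and alpha 0.01 gives 5.8% for the additive coefficient but only 20.3% for the interaction and 28.6% for ANCOVA. Most of that shortfall comes from how f is converted to a difference, which is a separate question.

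What the defence does not supply is an analysis instruction. A sample-size basis is not one, and here it conflicts with the ANCOVA in protocol 14.1. Preferring ANCOVA to the interaction is partly a matter of choice, but it is the protocol's own sizing analysis and the more powerful of the two.

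**Conclusion.** The gap is real. For ln(k), Q0, alpha and AUQ the SAP states neither a model nor a tested term, and three forms stand unreconciled: a mixed model with no named interaction, a baseline-adjusted ANCOVA, and a within-between interaction ANOVA.

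On the SAP's own sizing inputs the choice moves power at alpha 0.01 from 93% (ANCOVA) to 82% (interaction or post-only). It would fall to 29% if only the protocol's listed terms were fitted and the group coefficient were tested. At the SAP's analysis alpha of 0.05 the figures are 98%, 94% and 53%. The additive case would also halve the estimate, but it is a risk from loose wording and not what the documents commit to.

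These figures rest on a 1.0 SD difference in change (the value that reproduces 52), ρ = 0.5, equal expected baselines, equal variances and complete data. The ranking of ANCOVA first and the additive coefficient last does not depend on the exact effect size.

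**What to change.** Add to SAP, Objective 1: ln(k), Q0, alpha and AUQ at Session 5 are each analysed by ANCOVA with group, the same measure at a named pre-randomisation session, and the balancing variables (square-root drinks per day and baseline ln(k)). For ln(k), baseline ln(k) is entered once.

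The session must be named because assessments take place at both Session 2 and Session 3, and the text places randomisation within Session 3. The single-entry rule is needed because baseline delay discounting is itself a balancing variable.

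In protocol 5.2, keep the mixed model for daily drinks, add group × time and name it as the test, and refer the session-level measures to the ANCOVA. The cross-references under Delay discounting and Demand measures can then point to Objective 1.

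The cost is one SAP paragraph and one protocol line, with no new data. The change should be dated before outcomes are compared by group.

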4.0 Study Endpoints

*4.1 Describe the primary and secondary **study** endpoints. See links below for discussion of study endpoints and how they may differ from study objectives. These are most common in clinical trials but are sometimes applicable to other types of biomedical research, as well as social, behavioral, or educational research. See link below for a discussion.*

https://docs.google.com/document/d/1Wocz7K7a0hCQJPPO_khh511SQjhGDDGHzcOPRHR5Tw/edit?usp=sharing

Delay discounting: Change in discounting rates will be compared within-subjects between pre intervention and post intervention. In addition, differences in discount rates will be compared between groups (EFT and CET).

Alcoholic Drinks: Change in drinks per day and number of positive breath alcohol samples (BrAC) will be compared within-subjects between pre intervention and post intervention. In addition, differences in drinks per day and number of positive BrAC samples will be compared between groups (EFT and CET).

Alcohol Demand: Change in demand for alcohol will be compared within-subjects between pre intervention and post intervention. In addition, differences in alcohol demand will be compared between groups (EFT and CET).

Alcohol Craving: Change in alcohol craving will be compared within-subjects between pre intervention and post intervention. In addition, differences in alcohol craving will be compared between groups (EFT and CET).

4.2 *Describe any primary or secondary safety endpoints. These should be included for all studies that are greater than minimal risk. (Minimal risk: The probability and magnitude of harm or discomfort anticipated in the research that are not greater in and of themselves than those ordinarily encountered in daily life or during the performance of routine physical or psychological examinations or tests.):*

This study's procedures are not more than minimal risk.

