Height: Self report height

Penn Alcohol Craving Scale: Assesses alcohol craving.

Reward Responsiveness Scale: Measures responsiveness to reward through a single component measure

Timeline FollowBack Interview (TLFB): Assesses the number of alcoholic drinks and other substances daily for the past 30 days, or since the previous assessment, whichever is fewer.

Urinalysis: Assesses substance use and/or pregnancy.

Weight: Self report weight

**8.4 What data will you collect during the study and how you will obtain them?
Please include descriptions of electronic data collection, database matching, and app-based data collection:**

All of the survey and questionnaire data will be collected using Qualtrics, online survey platforms used to develop, administer, and collect participant data in a secure password protected database. Only study personnel will have access to the survey and collected data.

The fMRI tasks will be administered using python-coded tasks, wherein the participant data will be securely collected on a password protected shared-drive hosted by FBRI.

fMRI analyses. GLM-based analysis will be performed using AFNI. We will perform slice timing correction, motion correction, and spatial smoothing (Gaussian kernel with full-width-at-half-maximum of 2.0 Å~ the voxel size). Linear regression coefficients (beta-weights) and t-statistic maps will be calculated. Since fMRI relies on neurovascular coupling, which changes due to the vasoactive properties of alcohol, nicotine, and caffeine (short term) and for vascular damage (long term for AUD individuals), we will model our data with a finite impulse response basis set rather than a “standard” HRF model.

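### The SAP starts the intervention period at Session 2, so the 7-day pre-randomisation week enters the EFT v CET comparison of drinks and breath samples

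*SAP*

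**What the plan says.** **SAP, Data Measures, Alcohol Consumption.** The endpoint is a change: "Changes in drinks per day and the number of positive breath alcohol samples (BrAC) will be compared within subjects between pre-intervention and post-intervention". The section does not say which days form either side of it. Daily reporting is placed as follows: "During the intervention period (from Session 2 to Session 5), participants will report daily the number of alcoholic drinks consumed". The Timeline Follow Back (TLFB) interview "will be conducted during Session 2 (pre-intervention) and Session 6 (1-month follow-up) to assess the number of alcoholic drinks consumed daily".

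**SAP, Study design.** Baseline monitoring follows Session 2. Participants return for Session 3, are scanned, and are then randomised. Two 14-day monitoring phases follow, ending at Session 5.

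**SAP, Statistical Analyses, Objective 1.** Daily self-reported drinks during the intervention period are named as a primary measure, together with breathalyzer screens. Daily counts are compared between EFT and CET in a generalized linear mixed model. Breathalyzer results (positive or negative) are analysed by assignment over a field test of five weeks, allowing for time of day and repeated measures. Neither model is given a pre/post term. The Covariate Plan lists AUDIT score, SES, age and gender, but not baseline drinking. The Sensitivity Analyses refer to an intervention of four weeks.

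**Protocol 5.2.** Drinks are reported "on each day of the 7 day baseline and 28 day intervention period", and the model is a "mixed-effects hierarchical model that includes day, time (pre/post intervention), and intervention group".

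**The concern.** The two groups are treated alike until randomisation at Session 3, so the week between Sessions 2 and 3 carries no treatment effect. The SAP's definition nevertheless puts that week inside the intervention period, and the Objective 1 model compares the groups over that period with nothing to separate untreated days from treated ones. The breath-sample analysis has the same problem, because five weeks is the baseline week plus the four treated weeks.

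This is a stated rule that gives a diluted answer when followed, which is worse than an omitted detail. Randomisation is balanced on drinks per day, so the untreated week should not favour either arm. It pulls the estimated difference towards zero and costs power on the main consumption outcome. The SAP also promises a pre-to-post change without assigning days to pre and post, so the choice of windows is left to whoever runs the analysis.

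**Working it through.** **1. Day counts**
- Session 2 to Session 5 (SAP): 7 + 14 + 14 = 35 days, or five weeks. This matches the field test in Objective 1.
- Session 3 to Session 5: 14 + 14 = 28 days, or four weeks. This matches the SAP's Sensitivity Analyses and the 28-day intervention in protocol 5.2.
- Untreated share of the SAP's intervention period: 7/35 = 0.20.
- Breath samples at three per day: 21 of 105 precede randomisation, the same 0.20.

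**2. Dilution of the group difference**

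Let D be the true EFT v CET difference in drinks per day while cues are being sent. Assume D is constant over the 28 days and zero in the baseline week. The expected difference over 35 days is then

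(7 × 0 + 28 × D)/35 = 0.80 D.

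The same holds for a proportional effect. If EFT cuts the mean by a fraction r on treated days and the arms start equal, the 35-day ratio of means is 0.20 + 0.80(1 − r) = 1 − 0.80r.

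**3. Reproducing the SAP's sample size**

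Inputs from SAP, Sample size: f = 0.25, repeated-measure correlation 0.5, alpha 0.01, 80% power, within-between interaction with 2 groups and m = 2 measurements. The test is a noncentral F with 1 and N − 2 degrees of freedom and noncentrality

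λ = f² × N × m/(1 − ρ).

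At N = 52, λ = 0.0625 × 52 × 2/0.5 = 13.0 and power is 0.818. The smallest even N that reaches 80% is 52, so the SAP's figure reproduces.

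**4. Same calculation with the diluted effect**

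f = 0.80 × 0.25 = 0.20, so λ = 0.04 × 52 × 2/0.5 = 8.32.

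| Intervention period | f | Power, N = 52, alpha 0.01 | Completers for 80% power |
|---|---|---|---|
| Session 3 to 5 (28 days) | 0.25 | 0.82 | 52 |
| Session 2 to 5 (35 days) | 0.20 | 0.58 | 78 |

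The SAP's Statistical Principles set 0.05 as the significance level, with multiple-testing corrections. At an uncorrected 0.05 the corresponding powers are 0.94 and 0.81.

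**The case against.** The strongest reply is that the bracket is loose drafting. The SAP's design section calls the week after Session 2 baseline monitoring, its retention section refers to a baseline period of drinking, and its sensitivity section gives the intervention four weeks. A sensible analyst would read Session 2 to Session 5 as the span of daily reporting and would code pre and post at Session 3. With a day-level pre/post factor coded there and crossed with group, the dilution disappears. That is fair, and the 0.80 applies only to a period average or to a group effect without such a term. But the Objective 1 text describes a model of exactly that kind, relies on the mislabelled period, and for breath samples names five weeks outright. Protocol 5.2 lists a pre/post factor, but the SAP does not carry it over. Nor does the protocol state that post means the 28 days: that is inferred from the two collection periods it gives.

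A reader might infer something stronger: that the primary drinks result could be any of three quantities, because the Session 2 TLFB is the only drinks measure the SAP labels pre-intervention and the Session 6 TLFB is the only one after Session 5. The documents do not support this. Objective 1 names daily self-reports as the primary measure, and the SAP's Statistical Analyses section contains no TLFB analysis. Session 6 is labelled follow-up, and the endpoint sentence also covers breath samples, which have no TLFB counterpart.

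A reader might also infer that the TLFB recall windows conflict, since protocol 8.3 has "daily for the past 30 days, or since the previous assessment, whichever is fewer" and the SAP a fixed 30 days. On the SAP's schedule they agree. Session 2 has no earlier TLFB, and Session 6 falls 35 days plus a month after it, so both rules give 30 days.

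**Conclusion.** The SAP's intervention period is wrong by its own design section: it takes in the 7-day pre-randomisation week. Because Objective 1 compares the arms over that period with no pre/post term and no baseline-drinking covariate, the literal analysis estimates 0.80 of the treatment difference. On the SAP's planning inputs that is a fall in power from 0.82 to 0.58.

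These figures assume a constant effect over the 28 days, no effect in the baseline week, and unchanged SD and correlation. They use the SAP's two-measurement ANOVA as a yardstick; the power of the planned count model was not computed. The direction of the error, towards no difference, does not depend on that choice. The point is limited to the period definition, the unassigned pre and post days, and the missing model term. It does not extend to the choice of instrument for the primary outcome or to the TLFB recall window.

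**What to change.** All changes are to SAP wording.

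- **Alcohol Consumption, period:** start the intervention period at Session 3 instead of Session 2, ending at Session 5 as now.
- **Alcohol Consumption, windows:** define pre-intervention drinks and breath results as the daily remote data for days between Session 2 and Session 3, and post-intervention as those from Session 3 to Session 5. Assign each drinks report to the day of drinking it describes. Protocol 8.2 asks about the previous day, so the first report after Session 3 can refer to a day before randomisation.
- **Objective 1, model:** for both drinks and breath samples, bring in the baseline week only as the pre level of a pre/post factor interacting with group, or as a baseline covariate with the model confined to post-randomisation days. The protocol 5.2 model lists day, pre/post and group, so the first option needs only the interaction stated. Replace the five-week window in the breath-sample comparison accordingly.
- **TLFB:** state that Session 2 v Session 6 is a separate secondary follow-up comparison, and that TLFB and daily reports are not mixed in one change score.

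No new data, visits or participants are needed. The change should be made before anyone examines outcomes by arm.
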